**3. Version Date: 20-November-2015**

**4. Objectives:**

- To determine the impact of preoperative administration of tranexamic acid on blood loss and transfusion rates in major oncologic surgery.
- To evaluate the cost-effectiveness of tranexamic acid in major oncologic surgery.

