**8. Study Design:**

a. Recruitment Methods

Potential subjects will be recruited at their preoperative office visit with their surgeon or, if applicable, during their inpatient stay prior to surgery. Informed consent will be obtained by the Spectrum Health Oncology Research staff. The potential subjects include all patients scheduled to undergo major oncologic surgery that meet all of the

inclusion criteria, and none of the exclusion criteria. There will be no payment to study subjects. We plan to enroll a total of 200 subjects, unless planned interim analyses determine otherwise.

b. Inclusion Criteria

- Subjects undergoing major oncologic surgery for standard of care purposes (to include, but not limited to: liver resections, radical cholecystectomy, pancreaticoduodenectomy (Whipple procedure), esophagectomy, gastrectomy, colectomy, and debulking with hyperthermic intraperitoneal chemotherapy, prostatectomies, nephrectomies, and partial nephrectomies)
- Male or female  $\geq$  18 years of age
- Subject agrees to participate in this study and provides informed consent

Exclusion Criteria

- Subjects with a history of hypercoagulopathy, deep vein thrombosis or pulmonary embolism
- Subjects that are on anticoagulation or antiplatelet medications at the time of surgery other than Aspirin
- Subjects with a history of TIA or Stroke
- Subjects with a history of atrial fibrillation
- Subjects with a known thrombus
- Baseline creatinine level greater than 2.83 mg/dL
- Subjects with known hypersensitivity to tranexamic acid
- Adults unable to provide informed consent
- Children
- Pregnant women
- Prisoners
- Non-English speaking subjects
- Any other medical condition including mental illness or substance abuse deemed by the investigator to be likely to interfere with a subject's ability to provide informed consent, cooperate and take part in this research study

c. Study Endpoints

The primary outcome measures will be operative blood loss and transfusion rates in subjects undergoing the eligible procedures. Secondary outcome measures will include cost of hospitalization, intensive care unit length of stay, and total hospital length of stay.

d. Procedures Involved in the Research

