The study design will be a randomized, double-blind, placebo-controlled trial. Following satisfaction of inclusion/exclusion criteria and enrollment into the study, designated pharmacy staff will be notified of the patient's enrollment and scheduled timing of surgery. Designated pharmacy staff will randomize the patient and assign the patient a unique study number. The subject will be randomized based on a predetermined algorithm by the pharmacy staff to receive preoperative intravenous tranexamic acid or preoperative intravenous isotonic electrolyte solution as placebo. The preparation will be indistinguishable by nursing, surgical, or anesthesia staff. The tranexamic acid group will receive a 1000 mg dose immediately preceding surgery, administered by the anesthesiologist. Both the tranexamic acid and placebo will be administered via intravenous piggyback over 15 minutes. Standard daily

laboratory measurements will continue unless clinical conditions necessitate more frequent monitoring. Transfusion will take place for hemoglobin levels < 7.0 g/dL or hemoglobin level < 10 g/dL with clinical symptoms indicating need for transfusion, per standard practice. Final decision on transfusion will be made according to the staff surgical oncologist's discretion.

Data to be recorded from operative records will include operative blood loss, operative time, amount of fluid received, and intraoperative transfusion requirements. Postoperative data including hemoglobin levels, transfusion requirements, surgical complications, thromboembolic events, length of ICU stay, length of hospital stay, and cost of inpatient stay. Subjects will be followed for 90 days postoperatively. Additionally, re-admission to the hospital during this time will also be recorded with associated complications.

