### **b. Statistical Methods**

Summary statistics will be calculated. Quantitative data will be expressed as the mean $\pm$ SEM and nominal data will be expressed as a percentage. Comparisons between groups for quantitative variables will be performed using the t-test. Nominal variables will be evaluated using the  $c^2$  test. Significance will be assessed at  $p<0.05$ .

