## **15. Cost to Subjects**

Study drug, placebo, and preparation/administration will be paid for by funds allocated to the study, and not billed to the subjects. All other aspects of the subject's care are considered standard of care, and will be billed to the patient and/or their insurance company.

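### The cost-effectiveness objective has no matching analysis: inpatient cost is compared by t-test, never joined to transfusion, and the handling of study-paid drug and 90-day readmission costs is not stated

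*Combined protocol and SAP*

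**What the plan says.** Section 4 lists two objectives. The first concerns blood loss and transfusion; the second is "To evaluate the cost-effectiveness of tranexamic acid in major oncologic surgery".

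The later sections that bear on the second objective are these:

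- **8.c, endpoints.** "The primary outcome measures will be operative blood loss and transfusion rates in subjects undergoing the eligible procedures". Cost appears among the secondary outcomes: "Secondary outcome measures will include cost of hospitalization, intensive care unit length of stay, and total hospital length of stay".
- **8.d, data recorded.** The postoperative list ends with "length of hospital stay, and cost of inpatient stay". Follow-up is longer than the stay: "Subjects will be followed for 90 days postoperatively". Over that period, "re-admission to the hospital during this time will also be recorded with associated complications".
- **9.b, methods.** "Comparisons between groups for quantitative variables will be performed using the t-test". Quantitative data are summarised as mean and SEM.
- **Section 15, payment.** The infusion is funded by the study: "Study drug, placebo, and preparation/administration will be paid for by funds allocated to the study, and not billed to the subjects". The remaining care is billed in the usual way.

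No section names an effect measure to set against cost, a perspective, a time horizon for cost, a source for the cost figures, or a method for joint uncertainty in cost and effect.

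**The concern.** A cost-effectiveness question asks what is paid, or saved, for each unit of benefit. A t-test on cost asks only whether mean costs differ. A plan that stops at the second question leaves the first to be settled after the data are seen, including which effect to use and which costs to count.

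Two cost components are exposed to that choice. One is the intervention itself, which the study pays for. The other is readmission: the clinical horizon is 90 days, but cost is listed only with the inpatient stay. A partial cost difference could then be reported as a cost-effectiveness result.

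**Working it through.** **1. The plan's own figure.** The only design figure is 200 subjects, 100 per arm (9.a), based on an anticipated 15-20% reduction in transfusion. It cannot be reproduced uniquely, because the placebo rate, the power and the scale (absolute or relative) are not given. One reading that fits is 25% v 10%, two-sided 0.05, 80% power: n = [1.960 × √(2 × 0.175 × 0.825) + 0.842 × √(0.25 × 0.75 + 0.10 × 0.90)]² / 0.15² = (1.053 + 0.443)² / 0.0225 ≈ 100 per arm. No figure is stated for cost, so there is none to check.

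**2. From objective to analysis.**

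| Step | Section | Content |
|---|---|---|
| Objective | 4 | Cost-effectiveness |
| Endpoint | 8.c | Hospitalization cost, secondary |
| Data item | 8.d | Inpatient cost |
| Method | 9.b | t-test, as for any quantitative variable |
| Link to effect | none | Transfusion is analysed separately |

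The chain ends in a difference in mean cost.

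**3. What could be missing from that difference.** Write ΔC for mean cost on tranexamic acid minus placebo. Assume equal cost per readmission in the two arms. Then

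full ΔC = index-stay ΔC + D + Δr × c,

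where D is drug and preparation cost, Δr the difference in readmissions per subject (tranexamic acid minus placebo) and c the cost of a readmission. The documents give none of these, so the values below are assumptions.

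- *Drug.* D is positive, so leaving it out favours the drug by D per subject. With an assumed mean stay cost of 30,000 currency units and a coefficient of variation (CV) of 0.5 or 1.0, the standard error of ΔC is 30,000 × CV × √(2/100) = 2,121 or 4,243. D = 50 then shifts the test statistic by 50/4,243 = 0.01 to 50/2,121 = 0.02. D = 500 shifts it by 500/4,243 = 0.12 to 500/2,121 = 0.24.
- *Readmission.* With c at half an index stay, |Δr| of 0.02 to 0.05 gives 0.02 × 0.5 = 1% to 0.05 × 0.5 = 2.5% of index cost. With c = 20,000 and Δr from -0.05 to +0.05, the omitted amount runs from -1,000 to +1,000 per subject. The sign follows Δr, which is unknown.

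**4. Precision of the cost comparison.** With 100 per arm and 80% power, the detectable difference is (1.960 + 0.842) × √(2/100) = 0.396 SD. As a share of mean cost that is 20%, 40% or 59% at an assumed CV of 0.5, 1.0 or 1.5. The omissions illustrated in step 3 are small beside this.

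**5. Why a ratio alone would not repair it.** Let ΔE be the proportion transfused on placebo minus that on tranexamic acid. For 25% v 10%, SE = √(0.001875 + 0.0009) = 0.053, and the expected 95% interval is 15 ± 10.3 points. If the anticipated 20% is a relative reduction from the same assumed 25%, the rates are 25% v 20%, SE = √(0.001875 + 0.0016) = 0.059, and the interval is 5 ± 11.6 points, which includes zero. The ratio ΔC/ΔE then has no usable interval. It is also negative both when the drug saves money and spares transfusions and when it does the reverse, so its value does not separate the two cases. Net benefit, λ × ΔE - ΔC for a value λ per patient spared transfusion, has neither problem.

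**The case against.** The strongest case against the point has four parts.

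- **The question can be answered from planned data.** Transfusion and inpatient cost are both recorded per subject. This stands: a reader might infer that the objective cannot be met, and the documents do not support that. What is missing is the specified analysis.
- **Omission of the drug is an inference.** Section 15 governs what subjects are billed; 8.c and 8.d do not say whether cost comes from bills or from cost accounting. The drug is one preoperative dose, so its price is nearly a constant and can be added later. Placebo is also study-paid, so between the trial arms only the net amount drops out. All this stands, but no section says that the cost will be added, and outside the trial the alternative would be no infusion rather than placebo.
- **Readmission cost is not expressly excluded.** The inpatient cost item is not confined to the index admission. This is fair: the defect is that its scope is unstated.
- **The effect is small and the outcome secondary.** Section 5 calls the drug affordable, the illustrated omissions are minor against the precision for cost, and means with SEM already allow an interval for the cost difference. This stands as to size. It does not supply the missing link between cost and effect.

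A reader might also infer that the plan tilts towards the drug overall. That is not established. Sections 5 and 11 hope for fewer complications; if readmissions fall with them, leaving out their cost works against the drug.

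**Conclusion.** The concern holds in a limited form. The planned analysis does not answer the second objective, and this follows from the text without any assumption. The scope of the cost variable is unspecified for two components. Omitting the drug would favour it, but only if cost comes from bills, and by an amount that is not given and is probably small. Omitting readmissions could bias the comparison either way; 1 to 2.5% of index cost is an illustration on assumed inputs.

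A further tempting inference is that errors in cost are multiplied 5 to 7 times, since 1/0.20 = 5.0 and 1/0.15 = 6.7. That is only a change of unit, from per subject to per patient spared transfusion, and it reads the 15-20% as absolute, which 9.a does not say. Read as relative at an assumed 25% placebo rate, the reduction is 3.75 to 5 points and the same conversion gives 1/0.05 = 20 to 1/0.0375 = 27. It is not a measure of bias.

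The primary outcomes, the sample size and subject safety are unaffected. The plan should still be changed, because a stated objective lacks an analysis and the change is cheap.

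**What to change.** 1. **8.c.** Define cost per subject as the index admission plus readmissions to day 90, plus study drug and preparation at pharmacy acquisition cost in the tranexamic acid arm. State the source of the cost figures.
2. **8.d.** Add cost to the items recorded for each readmission.
3. **9.b.** Report the difference in mean cost and the difference in proportion transfused, each with a 95% interval, from a bootstrap that resamples subjects within arm so that each subject's cost and transfusion stay together. Summarise the two as net benefit over a range of values per patient spared transfusion, or on the cost-effectiveness plane. Give a cost per patient spared only if neither arm dominates and the transfusion difference is clearly away from zero.
4. **Alternative.** If this is not wanted, change the second objective in section 4 to a comparison of hospitalization cost.

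The choice should be fixed before cost is compared by arm, ideally before the first of the interim reviews in 8.f, whose findings go to the investigators. The cost is some wording, cost extraction for readmissions already recorded, and a modest amount of analysis. Sample size, treatment and follow-up do not change.

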**5. Background:**

Tranexamic acid was first introduced in the 1960's as a treatment for heavy menstrual bleeding. This medication inhibits fibrinolysis by inhibiting multiple plasminogen binding sites. In the past two decades, its use has been incorporated into surgical practice for patients undergoing open-heart surgery, liver transplantation, and urologic surgery. Recent reports of decreased mortality in patients with traumatic hemorrhage receiving tranexamic acid have shown significant promise. A 2006 study published out of Taiwan demonstrated decreased blood loss, reduced transfusion rates, and decreased overall hospital cost in patients undergoing liver resections for both benign and malignant conditions.

Major oncologic surgeries involving the liver and gastrointestinal tract involve extensive dissection, which can result in significant operative blood loss requiring intra- or postoperative transfusion. Tranexamic acid may be a useful addition in procedures with significant blood loss, as previous studies indicate it is both safe and affordable. While reports of seizure activity have been published when used at high doses (100 mg/kg), standard dosing regimens have proven to be safe and effective. The beneficial effect of reduction in bleeding has been demonstrated without an increase in thromboembolic events. We believe tranexamic acid has potential to reduce bleeding in major oncologic surgery resulting in reduced blood loss and lower transfusion rates. An improvement in the rate of surgical complications related to bleeding may also result in decreased hospital costs as well.

**6. Setting of the Research:**

Spectrum Health Butterworth Campus. Lemmen-Holton Cancer Pavilion.

**7. Resources Available to Conduct this Research:**

Approximately 15 major oncologic surgeries are performed on a monthly basis at the Spectrum Health Butterworth Campus. All individuals scheduled to undergo these surgeries that meet the eligibility criteria will be recruited for enrollment. Study personnel will include surgical residents with experience in surgical oncology research and knowledge of surgical outcome measures, with monitoring by a staff surgical oncologist.

**8. Study Design:**

a. Recruitment Methods

Potential subjects will be recruited at their preoperative office visit with their surgeon or, if applicable, during their inpatient stay prior to surgery. Informed consent will be obtained by the Spectrum Health Oncology Research staff. The potential subjects include all patients scheduled to undergo major oncologic surgery that meet all of the

inclusion criteria, and none of the exclusion criteria. There will be no payment to study subjects. We plan to enroll a total of 200 subjects, unless planned interim analyses determine otherwise.

b. Inclusion Criteria

- Subjects undergoing major oncologic surgery for standard of care purposes (to include, but not limited to: liver resections, radical cholecystectomy, pancreaticoduodenectomy (Whipple procedure), esophagectomy, gastrectomy, colectomy, and debulking with hyperthermic intraperitoneal chemotherapy, prostatectomies, nephrectomies, and partial nephrectomies)
- Male or female  $\geq$  18 years of age
- Subject agrees to participate in this study and provides informed consent

Exclusion Criteria

- Subjects with a history of hypercoagulopathy, deep vein thrombosis or pulmonary embolism
- Subjects that are on anticoagulation or antiplatelet medications at the time of surgery other than Aspirin
- Subjects with a history of TIA or Stroke
- Subjects with a history of atrial fibrillation
- Subjects with a known thrombus
- Baseline creatinine level greater than 2.83 mg/dL
- Subjects with known hypersensitivity to tranexamic acid
- Adults unable to provide informed consent
- Children
- Pregnant women
- Prisoners
- Non-English speaking subjects
- Any other medical condition including mental illness or substance abuse deemed by the investigator to be likely to interfere with a subject's ability to provide informed consent, cooperate and take part in this research study

c. Study Endpoints

The primary outcome measures will be operative blood loss and transfusion rates in subjects undergoing the eligible procedures. Secondary outcome measures will include cost of hospitalization, intensive care unit length of stay, and total hospital length of stay.

d. Procedures Involved in the Research

The study design will be a randomized, double-blind, placebo-controlled trial. Following satisfaction of inclusion/exclusion criteria and enrollment into the study, designated pharmacy staff will be notified of the patient's enrollment and scheduled timing of surgery. Designated pharmacy staff will randomize the patient and assign the patient a unique study number. The subject will be randomized based on a predetermined algorithm by the pharmacy staff to receive preoperative intravenous tranexamic acid or preoperative intravenous isotonic electrolyte solution as placebo. The preparation will be indistinguishable by nursing, surgical, or anesthesia staff. The tranexamic acid group will receive a 1000 mg dose immediately preceding surgery, administered by the anesthesiologist. Both the tranexamic acid and placebo will be administered via intravenous piggyback over 15 minutes. Standard daily

laboratory measurements will continue unless clinical conditions necessitate more frequent monitoring. Transfusion will take place for hemoglobin levels < 7.0 g/dL or hemoglobin level < 10 g/dL with clinical symptoms indicating need for transfusion, per standard practice. Final decision on transfusion will be made according to the staff surgical oncologist's discretion.

Data to be recorded from operative records will include operative blood loss, operative time, amount of fluid received, and intraoperative transfusion requirements. Postoperative data including hemoglobin levels, transfusion requirements, surgical complications, thromboembolic events, length of ICU stay, length of hospital stay, and cost of inpatient stay. Subjects will be followed for 90 days postoperatively. Additionally, re-admission to the hospital during this time will also be recorded with associated complications.

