## **9. Statistical Plan**

### **a. Sample Size Determination**

We anticipate a 15-20% reduction in transfusion rates in the tranexamic arm when compared with placebo treatment. A sample size of 200 total subjects, 100 in each arm of the study, will be required to obtain a statistically significant result with  $p <0.05$ . Randomization will ensure an equal number of respective surgeries between the treatment and placebo arms of the study. All subjects who consent to the trial who meet the above inclusion criteria and complete the proposed dosing regimen will be included in the sample size.

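### Two unranked primary outcomes are each tested at p<0.05 with no success rule; if either may carry the claim, the two-sided false-positive chance at the final analysis is about 7-10%, not 5%

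*Combined protocol and SAP*

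**What the plan says.** Study Endpoints (8.c) names two primary outcomes side by side: "The primary outcome measures will be operative blood loss and transfusion rates in subjects undergoing the eligible procedures". Objectives (4) pairs them in the same way: "To determine the impact of preoperative administration of tranexamic acid on blood loss and transfusion rates in major oncologic surgery".

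Statistical Methods (9.b) assigns tests by type of variable. For blood loss: "Comparisons between groups for quantitative variables will be performed using the t-test". For transfusion, the chi-square test applies: "Nominal variables will be evaluated using the" chi-square test. One threshold covers everything: "Significance will be assessed at" p<0.05. Sidedness is not stated.

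Sample Size Determination (9.a) considers transfusion only: "We anticipate a 15-20% reduction in transfusion rates in the tranexamic arm when compared with placebo treatment". It arrives at "A sample size of 200 total subjects, 100 in each arm of the study". It does not call transfusion the sole or leading primary outcome, and it gives no effect size or standard deviation for blood loss.

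No section gives a testing order, an alpha split, or a rule for what the trial concludes if the two outcomes disagree.

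**The concern.** With two primary outcomes, the error rate of the primary claim depends on how the two results are combined. The protocol leaves that open, so the rule could be settled after the data are seen.

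- **Either suffices:** there are two chances of a false positive, and the error at the final analysis exceeds 5%.
- **Both required:** the error stays at or below 5%, but the power is lower than for transfusion alone, the only outcome in the sample size section.

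Disagreement between the outcomes is realistic. Blood loss is an operative measure. Transfusion is recorded during and after surgery and depends on hemoglobin, symptoms and the surgeon's judgement. A significant blood-loss result with a non-significant transfusion result could be presented as primary success, although the trial was sized on transfusion. The protocol does not say whether that would be success.

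**Working it through.** **The plan's own figure.** The total of 200 cannot be reproduced: 9.a gives no control rate and no power, and does not say whether 15-20% is absolute or relative. With assumed rates, n = 100 per arm, p̄ the mean of the two rates, and power = Φ{[√n·|p1−p2| − 1.960·√(2p̄(1−p̄))] / √(p1(1−p1)+p2(1−p2))}:

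- 25% vs 10%: (1.5 − 1.053)/0.527 = 0.848, power 80%.
- 50% vs 35%: (1.5 − 1.370)/0.691 = 0.188, power 57%.
- 40% vs 32% (a 20% relative reduction): (0.8 − 1.330)/0.676 = −0.784, power 22%.

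Transfusion may therefore be well or poorly powered, depending on figures the plan does not give.

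**Inputs for the error rate.** Two primary outcomes (8.c); 0.05 for each (9.b). Assumed: two-sided tests (critical value 1.960), and a correlation r between the two test statistics from 0 to 0.9. Final analysis only, with no true effect on either outcome.

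**Either suffices.** Two-sided error = 1 − P(|Z1| ≤ 1.960 and |Z2| ≤ 1.960), with Z1 and Z2 bivariate normal. At r = 0 this is 1 − 0.95² = 9.75%. Counting only results that favour tranexamic acid, it is 1 − P(Z1 ≤ 1.960 and Z2 ≤ 1.960); at r = 0, 1 − 0.975² = 4.94%.

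**Both required.** By inclusion-exclusion, error = 0.05 + 0.05 − (either-suffices error). At r = 0: 0.10 − 0.0975 = 0.25%.

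**Holm.** With neither outcome affected, a false claim needs the smaller p-value to be below 0.025: 1 − P(|Z1| ≤ 2.241 and |Z2| ≤ 2.241). At r = 0: 1 − 0.975² = 4.94%.

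| r | Either, two-sided | Either, benefit direction | Both, two-sided | Holm, two-sided |
|---|---|---|---|---|
| 0 | 9.75% | 4.94% | 0.25% | 4.94% |
| 0.3 | 9.51% | 4.76% | 0.49% | 4.84% |
| 0.5 | 9.07% | 4.54% | 0.93% | 4.65% |
| 0.7 | 8.35% | 4.17% | 1.65% | 4.30% |
| 0.9 | 7.04% | 3.52% | 2.96% | 3.62% |

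The reference values are 5% two-sided and 2.5% in the direction of benefit. At r = 0.95 the either-suffices figures are 6.5% and 3.2%; the excess disappears only as r approaches 1. Under the both-required rule, if blood loss has a very large true effect and transfusion has none, the error rises to 5% but not above.

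**Check with the planned tests.** Simulating the t-test and chi-square test at 100 per arm (40,000 trials per setting, log-normal blood loss, assumed 30% transfusion rate) gave 8.3-9.9% two-sided and 4.1-4.8% in the direction of benefit, at test-statistic correlations of about 0 to 0.65. This agrees with the table.

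**Power under Holm.** An outcome with 80% power at 0.05 has mean z = 1.960 + 0.842 = 2.802. In the worst case it must pass at 0.025: Φ(2.802 − 2.241) = Φ(0.561), about 71%. If the other outcome also has about 80% power, Holm gives 76-77% for correlations 0.3-0.7. Requiring both to be significant gives 67-71% in the same setting.

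**Repeated looks.** If Holm were applied unchanged at 50, 100, 150 and 200 subjects (an assumption; 8.f gives no threshold), simulation gives a two-sided family error of about 13% at r = 0, 12% at r = 0.5 and 9.4% at r = 0.9.

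**The case against.** The strongest reply is that the plan never defines an overall success claim. The objective is to determine the impact on two outcomes; if each is reported on its own, each test keeps its own 5% error and no family-wise rate is breached. It can be added that the sample size makes transfusion the lead in practice. The first point stands as a limit: the inflation is conditional on an either-suffices reading. The second is an inference. Section 9.a does not rank the outcomes, and 4 and 8.c both list blood loss first. Neither reply supplies the missing rule.

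A second reply is that blood loss and transfusion are related, so zero correlation, which produces the 10% end, is the least plausible case. That is fair, and it is why a range is given. But transfusion also turns on symptoms and discretion, which makes a correlation near 1 unlikely, and at 0.9 the figure is still 7%.

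A third reply is that Holm is only one choice. That also stands: a fixed order, or requiring both, would close the gap equally well.

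**Conclusion.** The gap is real and should be closed: there are two unranked primary outcomes, one threshold for each, and no success rule. If either outcome may carry a claim of benefit and neither is truly affected, the chance of at least one false primary finding at the final analysis is about 7-10% two-sided against 5%. The range rests on two-sided testing and a correlation of 0.9 down to 0, both assumed.

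Three stronger readings are not supported:

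- A reader might infer that the plan as written has a 7-10% error rate outright. The documents do not adopt an either-suffices rule; they give no rule.
- A reader might take 2.5% as the plan's error level and cite 3.5-4.9% against it. Section 9.b states only p<0.05. The 2.5% follows only if tests are two-sided and only results favouring tranexamic acid count.
- A reader might infer that a Holm rule would settle all multiplicity in this trial. Section 8.f plans unblinded reviews for significance after every 50 subjects with no alpha rule. Holm at the final analysis does not cover them, and the 7-10% does not include them.

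**What to change.** Before any unblinded review, state one success rule in 8.c and 9.b. Wording that keeps both stated primaries:

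> Operative blood loss and transfusion rate are both primary outcomes. At the final analysis, the smaller of the two primary p-values is tested at two-sided 0.025. If it is significant, the other is tested at two-sided 0.05; if not, neither is claimed. The conclusion is limited to the outcome or outcomes that pass. These levels apply to the final analysis only; the interim reviews in 8.f follow a separate alpha rule.

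The sponsor could instead test transfusion first and blood loss second, each at 0.05, which gives blood loss a lower rank than the stated objective does. Or it could require both to be significant, at a larger cost in power. Whichever rule is chosen, the alpha rule for the reviews in 8.f must be written separately and made consistent with it.

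The cost is a protocol amendment, no extra subjects and, under Holm, the modest loss of power shown above: from 80% to no lower than about 71%, or to 76-77% when the other outcome also has about 80% power.
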